### **6.3 PHARMACODYNAMIC AND PHARMACOKINETIC ANALYSIS**

#### **6.3.1 VerifyNow for aspirin and P2Y12 analysis**

VerifyNow™ (Accumetrics, San Diego, California, USA) is a near patient test comprising a turbidimetric based optical detection system that measures platelet aggregation as an increase in light transmittance.

We are already using this system for clinical research in our department and it has FDA approval for the assessment of Aspirin and P2Y12 activity. VerifyNow has also been used in the assessment of ticagrelor activity in a number of studies (17, 25, 26). 2 ml of whole blood is transferred into a Greiner Bio-One Vacuette containing 3.2% sodium citrate (Accumetrics, San Diego, California, USA) and inverted carefully, after which the tube is left at room temperature for a minimum of 15 and 30 minutes for both P2Y12 and aspirin assays respectively. The tube is then loaded into a specific assay device and analysed as per the manufacturers' instructions (Accumetrics). The system is calibrated daily electronically and full quality control is performed with each batch of assay devices. This system uses a similar principle to formal platelet aggregometry. Arachidonic acid is used in the aspirin assay, ADP in the P2Y12 assay. Aspirin will already have been given in the

ambulance and its antiplatelet effect will be assessed at 20 minutes and 60 minutes after the P2Y12 inhibitor loading dose

Results are shown as aspirin response units (ARU) and P2Y12 reaction units (PRU) for aspirin and P2Y12 assays respectively.

### **6.3.2 VASP flow cytometry**

VASP, an intracellular actin regulatory protein, is a substrate of both cyclic adenosine monophosphate (cAMP)- and cyclic guanosine monophosphate (cGMP)-dependent protein kinases (27). Dephosphorylation of VASP follows P2Y12 stimulation. Conversely, inhibition of the P2Y12 receptor by clopidogrel and stimulation of prostaglandin E1-activated adenylyl cyclase induce phosphorylation of VASP by cAMP-dependent protein kinases. Thus levels of VASP phosphorylation/dephosphorylation reflect P2Y12 inhibition/activation.

Despite using a commercially available assay (Biocytex, Asnieres, France), VASP flow cytometry is primarily a research based assessment owing to the complexity of the procedure and the requirement for significant technical expertise. It is seen by some as a gold standard test for P2Y12 inhibition.

Whole blood transferred to tubes containing 3.2% sodium citrate is incubated with PGE1 or PGE1 and ADP for 10 minutes then fixed with paraformaldehyde, then platelets are permeabilized with non – ionic detergent. The cells are than labelled with a monoclonal antibody against 239-phosphorylated VASP and then a secondary fluoroscein isothicyanate-conjugated polyclonal antibody. Analysis will be performed on a Becton Dickinson (Plymouth, UK) FACS Calibur flow cytometer, and 10,000 platelets will be gated per assessment as per the manufacturer's instructions. Results are expressed as percentage platelet reactivity index (% PRI). VASP flow cytometry will be performed within 48 hours of sampling.

VASP Flow cytometric analysis measures activity at the P2Y12 receptor very effectively and thereby indirectly the activity of P2Y12 inhibitor and has been shown to be of value in a number of clinical trials including one carried out by our own research group (28, 29).

### **6.3.3 Liquid chromatography with tandem mass spectrometry.**

We will be using this technique to quantify the active metabolites of prasugrel, and ticagrelor. The active metabolite of prasugrel are not stable in blood, therefore 3'-methoxy-phenacylbromide (an alkylating reagent) will be added within 30 seconds of sampling to whole blood collected in EDTA tubes to derivatize and stabilize the metabolites. Derivatized blood samples will be centrifuged at 1500g for 10 minutes. The plasma will be extracted and frozen at -80C until analysis.

Blood samples for ticagrelor active metabolite quantification will be collected in lithium heparin tubes. The active metabolites of ticagrelor are stable in blood, thus require no

stabilization. The blood samples will undergo the same processing and storage protocol as highlighted above.

The derivatized and ticagrelor plasma samples then undergo solid phase extraction and are then separated using liquid chromatography and quantified using mass spectrometry. The primary pharmacokinetic parameters (i.e. the active metabolites of prasugrel, and ticagrelor) are calculated using the maximum observed concentration ( $C_{max}$ ) and area under the plasma concentration curve (AUC). This technique has already been developed and validated used previously to detect the active metabolite of either prasugrel and ticagrelor in a number of publicized studies (30-34).

To summarize, each sample will be used for

- 1) P2Y12 inhibition estimation using the near patient Accumetrics VerifyNow test
- 2) P2Y12 inhibition will also be estimated by Flow Cytometry using VASP phosphorylation test.
- 3) Aspirin effect using near patient Accumetrics VerifyNow test.
- 4) The active metabolites of prasugrel and ticagrelor will be measured using liquid chromatography with mass spectrometry.

Time	Pre Dosing	20 Min post dosing	Balloon Time (PPCI)	60 min post dosing	4 hrs post dosing
Procedure	Consent	15 ml blood	15 ml blood	15 ml blood	15 ml blood
VN Aspirin		x	X	x	
VN P2Y12		x	X	x	X
VASP Phosphorylation		x	X	x	X
Estimation of active metabolite		x	X	x	X

## 7. STATISTICS AND DATA ANALYSIS

All statistical analysis will be performed in collaboration with [name], Professor of biomedical statistics at University of Wolverhampton.

Continuous variables will be compared using parametric and non-parametric tests as appropriate. Dichotomous variables will be compared by Fishers exact test. Logistic regression analysis will be used to predict the significant independent predictors of poor outcome post angiography.

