### **3. STUDY OBJECTIVES**

- 1) To determine the degree and time-course of platelet inhibition in patients admitted with NSTEMI treated with prasugrel within the first 4 hours of loading. These data will be compared with data already collected on STEMI patients treated with prasugrel to determine whether the condition of STEMI per se reduces the efficacy of prasugrel treatment.
- 2) To demonstrate the degree and time-course of platelet inhibition by ticagrelor given acutely before emergency primary angioplasty for STEMI, during the procedure and in the following 4 hours. This will be compared with a cohort of patients presenting with NSTEMI treated with ticagrelor to determine whether the condition of STEMI per se reduces the efficacy of ticagrelor treatment.

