## 4. STUDY DESIGN

This is a pilot study which is both non-randomised and observational in nature. We plan on recruiting a total of 45 participants into the study who will comprise of patients admitted to New Cross Hospital suffering from an acute coronary syndrome. The study will complete an on-going project (REC ref no. 13/WM/0025 ethical approval granted from South Birmingham Regional Ethics Committee). Whole blood samples will be taken from participants following a single loading dose of an antiplatelet agent once the diagnosis of an ACS has been made. We anticipate the conclusion of subject recruitment in 3 months from the study start date

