### 4.1 STUDY OUTCOME MEASURES

- a) Degree of platelet inhibition measured with VerifyNow™ rapid platelet function analyser
- b) Degree of platelet inhibition measured with VASP flow cytometry
- c) Concentration of prasugrel and ticagrelor active metabolite in plasma measured with liquid chromatography with tandem mass spectrometry.

This study is not powered for clinical outcomes; however clinical data will be recorded.

Clinical endpoints to be recorded for each participant will include:

- d) Angiographic variables –
  - thrombolysis in myocardial infarction (TIMI) flow at end of case,
  - slow flow/no reflow
- e) ECG variables –
  - ST-segment resolution at end of case
- f) Safety endpoints –
  - Death
  - CABG
  - TIMI major and minor bleed (see appendix 1 for bleeding criteria)

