### **5.2 PRE-REGISTRATION EVALUATIONS**

All research subjects will be identified from STEMI patients admitted for PPCI at the Heart and Lung Centre in Wolverhampton and also UA/NSTEMI acute coronary syndrome patients admitted to New Cross Hospital, Wolverhampton. Patient groups (below) are carefully selected so that all patients will receive anti-platelet drugs as per current accepted National and local guidelines and as per the manufacturers' datasheets.

- 1) Group 2: Patients with NSTEMI who are under 75 years of age and greater than 60Kg in weight receiving Prasugrel loading (60mg) however: -
  - i. After sample collection patients treated with intracoronary stent placement on the same day as loading will receive prasugrel maintenance dose (10mg per day) as per licensing agreement for prasugrel
  - ii. After sample collection patients who are not stented after loading will receive clopidogrel maintenance dose (75mg per day).
- 2) Group 5: Patients admitted with STEMI receiving ticagrelor loading (180 mg) and then maintenance (90mg bd per day).

- 3) Group 6: Patients Admitted with NSTEMI receiving ticagrelor loading (180 mg) and then maintenance (90mg bd per day).

We plan to recruit 15 patients into each group.

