### **5.3 INCLUSION CRITERIA**

- 1) Patients presenting with STEMI for PCI (characterized by chest discomfort, and prominent ST-segment elevation)
- 2) Patients presenting with NSTEMI (characterized by chest discomfort, raised levels of myocardial enzymes and/or ST-segment depression or prominent T wave inversion)
- 3) Able to give verbal consent (STEMI patient's pre procedure) and/or written consent (STEMI after procedure and NSTEMI patients prior to enrolment).
- 4) Age > 18 years of age
- 5) Able to take Aspirin and either prasugrel or ticagrelor.
- 6) Have no concurrent septic or inflammatory illness
- 7) Thienopyridine naive

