## **6. ASSESSMENT AND FOLLOW-UP**

**6.1 Subjects:** A total of 45 subjects will be included in the study of which 15 patients will undergo PPCI as part of the treatment for STEMI.

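### The planned logistic search for independent predictors of poor outcome cannot be relied on in a 45-patient pilot at moderate effects or low event counts; report the clinical endpoints descriptively

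*Combined protocol and SAP*

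**What the plan says.** Section 7 (Statistics and Data Analysis) names one multivariable analysis: "Logistic regression analysis will be used to predict the significant independent predictors of poor outcome post angiography". It does not say which endpoint counts as a poor outcome, which predictors are candidates, how they are selected, at what significance level, or in which patients. The same section assigns dichotomous variables to Fisher's exact test.

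Other sections set the context:

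- Section 6.1 gives the size: "A total of 45 subjects will be included in the study of which 15 patients will undergo PPCI". Section 5.2 plans 15 patients in each of three groups.
- Section 4.1 lists end-of-case TIMI flow, slow flow or no reflow, ST-segment resolution, death, CABG and TIMI bleeding, and says: "This study is not powered for clinical outcomes; however clinical data will be recorded".
- Both objectives in Section 3 concern platelet inhibition. The first begins "To determine the degree and time-course of platelet inhibition in patients admitted with NSTEMI treated with prasugrel"; the second asks the same kind of question for ticagrelor.
- Section 4 calls the study a non-randomised, observational pilot and adds: "The study will complete an on-going project". Section 7 does not say that data from that project enter the logistic model.

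**The concern.** A search for significant and independent predictors, in the plural, is a multivariable model read by p-value. How well it works depends mainly on the number of events, and 45 patients may supply few. Three things can go wrong: true predictors are missed, null candidates are declared significant, and the odds ratios that pass the significance filter are too large. Section 7 does not label the analysis exploratory, and Sections 8 and 12 foresee a journal article. A claimed predictor of poor outcome could therefore be published from a study that says it has no power for clinical outcomes, to answer a question that its objectives do not ask.

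**Working it through.** **Inputs from the documents.** Total 3 × 15 = 45, which agrees with Sections 4 and 6.1; 15 patients with PPCI. There is no power calculation for the logistic model to reproduce.

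**Assumptions, none given in the documents.** Event rate 10, 20, 30 or 50%; five candidate predictors (two as a sensitivity case); true odds ratio 2 or 3 per SD; two-sided 5% tests; correlation 0 or 0.7 between the two true predictors.

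**1. Expected events** (patients × rate), all 45 patients:

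- 45 × 0.10 = 4.5
- 45 × 0.20 = 9
- 45 × 0.30 = 13.5
- 45 × 0.50 = 22.5

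**2. Finding two true predictors among five.** Simulated logistic models, n = 45, standard normal predictors, intercept set to give the stated marginal rate. Runs without a finite fit count as not found. The table shows the share of studies in which both true predictors are significant by likelihood-ratio (LR) test:

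| Event rate | OR 2 per SD | OR 3 per SD |
|---|---|---|
| 10% | about 8% | about 16–21% |
| 20% | about 19% | about 45% |
| 30% | about 25% | about 60% |
| 50% | about 32% | about 70% |

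Wald tests do worse: at OR 2 about 10% and 16% at rates of 20% and 30%. If the two true predictors correlate at 0.7, both are found in about 2–3% of studies (LR, OR 2).

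**3. False positives when every candidate is null**, n = 45. The nominal chance of at least one is 1 − 0.95^k: 22.6% for k = 5 and 9.75% for k = 2.

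| Null candidates | LR | Wald |
|---|---|---|
| Five | about 25–31% | about 7–23% |
| Two | about 9–12% | about 5–9% |

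Most of this is ordinary multiplicity. The LR test adds some small-sample excess; the Wald test is at or below the nominal figure.

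**4. One predictor only**, n = 45, rates 20/30%. At OR 2 per SD, power is 44/51% (LR) or 37/45% (Wald). The median odds ratio among Wald-significant results is 3.23/2.85, an inflation of 3.23 ÷ 2 = 1.6 and 2.85 ÷ 2 = 1.4 times. At OR 3 per SD, power is 75/84% (LR).

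**5. Larger totals, if earlier data were pooled** (sizes assumed; LR; rates 20/30%). At OR 2, uncorrelated, both true predictors are found in 29/38% at n = 60 and 45/61% at n = 90. At OR 3 and n = 90 the figure is about 93% at a 30% rate.

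**6. What descriptive reporting delivers.** Exact 95% intervals: 0/15 gives 0–21.8%; 3/15 gives 4.3–48.1%; 0/45 gives 0–7.9%; 9/45 gives 9.6–34.6%. They are wide, but available at any event count.

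**The case against.** The strongest reply is that the size of the problem is assumed. Section 7 states no number of candidates, and the documents give no event rate for any listed endpoint. Incomplete ST-segment resolution or impaired flow could be common. With two strong predictors (OR 3 per SD) and a 50% rate, both are found in about 70% of studies, and with two candidates instead of five the false-positive risk is near nominal. This stands. It limits the conclusion to moderate effects or low event counts, and rules out any flat statement that the model will usually miss real predictors or often produce false ones.

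Second, the study completes an earlier project, so a larger combined data set is plausible and would help, decisively so with strong effects. But Section 7 does not plan pooling for this model, and the documents give no size for the earlier data.

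Third, exploratory regression is normal in a pilot. That is fair, and the fix leaves room for it. Section 7, however, neither labels this model exploratory nor restricts it.

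Three stronger readings are tempting but not supported:

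- *The model would be run in the 15 PPCI patients and might have no finite fit.* Section 7 speaks of outcome after angiography and names no such subset. Section 5.2 mentions "patients who are not stented after loading" in the NSTEMI prasugrel group, but a patient without a stent may still have had angiography.
- *The follow-up times contradict each other.* Section 5.1 ends participation at the 4-hour sample, and Appendix 1 uses 7 days for fatal bleeding. The 7 days classify a bleed as fatal; they do not set a follow-up period. What is missing is a stated ascertainment time.
- *Collinearity is built in because VerifyNow and VASP both estimate P2Y12 inhibition.* Section 7 names neither as a predictor. The correlated case is a sensitivity check only.

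**Conclusion.** The concern holds in a limited form. In 45 patients, a set of independent predictors of clinical outcome cannot be reliably identified at moderate effects (OR about 2 per SD) at any event rate examined, or at low event counts even with strong effects. Odds ratios that reach significance at moderate effects are inflated, by about 1.4–1.6 times for one continuous predictor with OR 2 per SD. A single strong predictor of a common outcome could be detected.

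All of these figures rest on assumed event rates, effect sizes, candidate counts and predictor distributions. What does not rest on them is the mismatch in the documents: a significance-based predictor search in a study that disclaims power for clinical outcomes and whose objectives do not call for it. The change should be made because it is cheap, but the point lies outside the main objectives and does not threaten them.

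**What to change.** Replace the logistic regression sentence in Section 7 with:

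> *Clinical endpoints will be summarised per group as counts with exact 95% confidence intervals, giving the denominator observed for each endpoint, without significance testing; no multivariable search for predictors of clinical outcome will be done.*

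The words on significance testing are needed because Section 7 would otherwise still apply Fisher's exact test to dichotomous clinical endpoints.

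If a model is kept, limit it to one pre-named predictor of one defined binary outcome in a stated set of patients. Fit it by a Firth or exact method, report the estimate with its confidence interval, and label it exploratory. If earlier groups are to be pooled, say so and give their size.

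Separately, state the time to which death, CABG and bleeding are ascertained.

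The cost is one replaced sentence and one added time point. The downside is that an exploratory analysis outside the objectives is lost or reduced to a single predictor. Recruitment, sampling and the platelet-inhibition analyses are unaffected.

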## 8. END OF STUDY

The study will come to an end when the participant recruitment target has been met, all samples have been analysed and the data has been scrutinised, and finally an article

summarising the study written and submitted to a peer reviewed journal for consideration of publication.

## 9. ADVERSE EVENTS

### 9.1 DEFINITIONS

**9.1.1 Adverse Event (AE):** any untoward medical occurrence in a patient or clinical study subject.

**9.1.2 Serious Adverse Event (SAE):** any untoward and unexpected medical occurrence or affect that:

- **Results in death**
- **Is life-threatening** – *refers to an event in which the subject was at risk of death at the time of the event; it does not refer to an event which hypothetically might have caused death if it were more severe*
- **Requires hospitalisation, or prolongation of existing inpatients' hospitalisation**
- **Results in persistent or significant disability or incapacity**
- **Is a congenital anomaly or birth defect**

Medical judgement should be exercised in deciding whether an AE is serious in other situations. Important AEs that are not immediately life-threatening or do not result in death or hospitalisation but may jeopardise the subject or may require intervention to prevent one of the other outcomes listed in the definition above, should also be considered serious.

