### 9.2 REPORTING PROCEDURES

All adverse will be reported. Depending on the nature of the event the reporting procedures below will be followed. Any questions concerning adverse event reporting will be directed to the Chief Investigator in the first instance.

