#### 9.2.1 Non serious AEs

All such events, whether expected or not, will be recorded.

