#### 9.2.2 Serious AEs

An SAE form will be completed and faxed to the Chief Investigator within 24 hours. However hospitalisations for elective treatment of a pre-existing condition do not need reporting as SAEs.

Information about all serious adverse events will be collected and recorded on the Serious Adverse Event Report Form and faxed to the R&D Directorate at New Cross Hospital within 24 hours of learning of its occurrence.

All serious adverse events will be reported to the appropriate regulatory and ethical authorities.

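### Section 9.1.2 makes unexpectedness part of the SAE definition, so the prompt and external reporting in 9.2.2 is not clearly required for an expected serious event

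*Combined protocol and SAP*

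**What the plan says.** Section 9.1.1 defines an adverse event as "any untoward medical occurrence in a patient or clinical study subject". Nothing in that definition depends on whether the event was foreseen.

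Section 9.1.2 defines a serious adverse event as "any untoward and unexpected medical occurrence or affect that" meets one of the criteria that follow: death, threat to life, hospitalisation or a longer stay, lasting disability, or congenital anomaly. The criteria all sit under that opening phrase. Two further sentences follow the list. The first is "Medical judgement should be exercised in deciding whether an AE is serious in other situations". The second begins "Important AEs that are not immediately life-threatening or do not result in death or hospitalisation but may jeopardise the subject" and ends by saying that such events should also be treated as serious.

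On reporting, section 9.2 opens with "All adverse will be reported" (the noun is missing) and then sends each event to a procedure according to its nature. For non-serious AEs, section 9.2.1 says "All such events, whether expected or not, will be recorded". For serious AEs, section 9.2.2 says "An SAE form will be completed and faxed to the Chief Investigator within 24 hours", requires the information on all of them to be "faxed to the R&D Directorate at New Cross Hospital within 24 hours of learning of its occurrence", and requires all of them to go to the relevant regulatory and ethical bodies. It exempts elective admissions for a pre-existing condition.

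Section 4.1 lists death, CABG and TIMI bleeding as safety endpoints recorded for each participant.

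**The concern.** Seriousness describes the outcome of an event. Expectedness describes whether it was foreseen. Section 9.1.2 joins the two, so a grave event can fall outside the SAE definition only because someone judged it foreseeable. In the available text, the deadlines and named recipients appear only in 9.2.2, and that section applies to SAEs. An event that fails the definition therefore has no stated deadline and no stated recipient.

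The population is acute myocardial infarction treated with potent antiplatelet drugs, some of it with emergency angioplasty. Known complications of the disease and the procedure are the events most open to being called expected. The available text gives no list of expected events, no definition of the term, and no one named to make the judgement. What is at stake is whether such an event must be reported promptly and outside the study team. Whether it is recorded at all is not in doubt.

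**Working it through.** No arithmetic applies. The check is to follow an expected event that meets a listed criterion, taking death as the example, through each clause.

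1. **Is it an AE (9.1.1)?** Yes. The definition has no expectedness condition.

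2. **Is it an SAE by the main definition (9.1.2)?** No. The event must be untoward, and unexpected, and meet a criterion. It fails the second condition, so meeting the third does not help.

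3. **Does the medical-judgement sentence bring it in?** Not clearly. It applies to situations other than those listed, and death is listed. Even read more widely, it permits a classification and does not require one.

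4. **Does the sentence on important AEs bring it in?** It speaks of AEs, so it carries no expectedness condition, but its scope depends on how its *or* is read.
   - If *or* means that none of the named outcomes applies, the sentence covers only events that were not immediately life-threatening, not fatal, and did not lead to hospitalisation. An expected death stays outside. An expected disabling event without those outcomes could come in.
   - If *or* means that either limb is enough, an expected event that was not immediately life-threatening but later proved fatal could come in, provided it jeopardised the subject or might have required intervention. An event that was both immediately life-threatening and fatal would still be outside.
   - On either reading some expected events return and some do not, and the text does not say which reading is meant.

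5. **Does the opening of 9.2 close the gap?** No. It promises reporting but sets no deadline and names no recipient. It passes the event on to 9.2.1 or 9.2.2.

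6. **Which route then applies?** If the event is not an SAE, 9.2.1 applies and it is recorded. If it is an SAE, 9.2.2 applies, with two 24-hour reports and the report to the authorities. The explicit statement that expectedness does not matter appears in 9.2.1 only.

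7. **Does 9.2.2 agree with the definition?** Not comfortably. It speaks of all serious adverse events and exempts elective admissions by name. That exemption would hardly be needed if expected events were already excluded by definition. Section 9.2.2 therefore reads as if expectedness were not part of the SAE definition, while 9.1.2 makes it part.

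Result: an expected event that meets a listed criterion is captured as an AE and, if fatal, as an endpoint under 4.1. Its place in the 9.2.2 procedure is not clear.

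**The case against.** The strongest reply is that this is a drafting slip with almost no practical reach. Section 9.2.2 covers all serious adverse events, no expected events are listed, and an investigator would have little basis in the document for labelling a death expected and withholding the form. The drugs are licensed and given as part of normal care, pre-existing cardiogenic shock is an exclusion, and the study is a small observational pilot. Most of this stands, and it is why the point is rated low. It does not remove the mismatch: the reporting rule takes its scope from the definition, and the definition contains the word.

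A second reply is that the sentence on important AEs rescues these events. It may rescue some, as step 4 of the working shows. A reader might infer that every expected death is plainly cut off from 9.2.2. The loose *or* in that sentence does not allow so firm a statement. The supportable claim is that such deaths are not clearly routed.

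A reader might also infer that the Trial Management Committee would be left uninformed, since section 11 provides no Data Monitoring Committee and gives the safety role to that body. The documents do not support this. Section 11 speaks of adverse events of a particularly serious type and does not use the SAE definition. Section 9.2.2 does not name the committee as a recipient. Nothing in the available text makes 9.2.2 the committee's source of information.

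Finally, the text between 9.2.2 and 10.2 was not available. If it contains further reporting rules, it could settle the question. That reservation applies to the whole point.

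**Conclusion.** The point holds as a low-severity inconsistency between the SAE definition and the SAE reporting rule. As written, the 24-hour reports to the Chief Investigator and the R&D Directorate, and the report to the authorities, are not clearly required for an expected event that meets a seriousness criterion, including death. The inclusion of the word is probably unintended.

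A reader might infer that expected deaths would go unrecorded. They would not: sections 4.1, 9.2 and 9.2.1 between them capture them.

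The size cannot be expressed as a number of events. The documents list no expected events and give no rate of expected serious events, so any count would rest on invented inputs. The platelet-function and pharmacokinetic results are not affected. The conclusion assumes that 9.1.2 is applied literally and that the unavailable text before 10.2 does not add a rule that resolves it.

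**What to change.** Delete the words 'and unexpected' from the opening phrase of 9.1.2, so that an event is serious because of its outcome alone. Section 9.2.2 then works as it reads. If the sponsor intends expectedness to limit what goes to the regulatory and ethical bodies, that limit belongs in 9.2.2, stated as a condition on external reporting and not on seriousness.

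The cost is a two-word deletion, or that deletion plus one sentence in 9.2.2. The downside is some extra SAE forms, for example for foreseeable prolonged hospital stays. The documents do not allow these to be counted, but the planned total of 45 participants suggests a modest burden. The existing exemption for elective admissions can stay as it is.
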